6.2 Baseline

For the primary endpoint, baseline will be defined in 3 ways: 1.) the average between the screening and the day 1 visits. If either is missing, the non-missing value will be considered baseline for this approach. This is the primary definition for the study 2.) The Day 1 value or the last value prior to first dose of study drug. 3.) The value from the screening visit as the baseline. The primary endpoint will be evaluated using all 3 baseline calculations. For all secondary and safety endpoints, baseline will be defined using method 2.) above.

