#### **7.1.3 Baseline Visit (Day1)**

Subjects who meet all inclusion criteria and none of the exclusion criteria will report to the clinic on the morning of Study Day 1 after fasting overnight for a minimum of 8 hours. After a review

of applicable inclusion/exclusion criteria, subjects who continue to satisfy eligibility requirements will be randomized in a 3:3:1 ratio to their treatment group. Predose assessments and procedures will be conducted as noted in the SoA (Appendix 1) and considered Baseline values.

After predose/Baseline study procedures are completed, subjects will receive the first dose of study drug in the clinic on Day 1 followed by PK and biomarker blood draws. Additional PK, C4, FGF19 and Bile Acid samples will be collected from subjects at a subset of sites (PK/PD Substudy) that have the technical capability to collect and process intensive (longer duration) sampling. PK and PD samples will be collected as described in Section 8.4.

Before leaving the clinic, subjects will receive study medication and instructions on how to take the medication at home.

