### 10.2 Management of Liver Enzyme Elevations

The FDA Guidance for Industry for Drug Induced Liver Injury (FDA, 2009) will provide guidance for the management of changes in liver transaminases (ALT/AST) and TB.

The protocol also includes an algorithm to respond to changes in liver enzymes and functions as follow:

- To establish a baseline utilizing at least 2 lab values at least several weeks apart.
- For subjects with elevated baseline liver chemistry that develop AST or ALT elevations  $2 \times$  baseline, subjects will be reassessed promptly (eg, 48-72 hours) with full liver biochemistry and physical exam and if the repeat assessment shows persistent elevations in transaminases, subjects should be followed according to the “close observation” guidelines:
  - Repeat liver enzyme and serum bilirubin tests two or three times weekly. Frequency of repeat testing can decrease to once a week or less if abnormalities stabilize or the trial drug has been discontinued and the subject is asymptomatic.
  - Collect additional PK samples at the same visits as safety labs
  - Obtain a more detailed history of symptoms and prior or concurrent diseases.

- Obtain a history of concomitant drug use (including nonprescription medications and herbal and dietary supplement preparations), alcohol use, recreational drug use, and special diets.
  - Rule out acute viral hepatitis types A, B, C, D, and E; autoimmune or alcoholic hepatitis; NASH; hypoxic/ischemic hepatopathy; and biliary tract disease.
  - Obtain a history of exposure to environmental chemical agents.
  - Obtain additional tests to evaluate liver function, as appropriate (eg, INR, direct bilirubin).
  - Consider gastroenterology or hepatology consultations.
  - Consider liver biopsy for any patient with persistent evidence of liver injury.
- If a subject lives in a remote area, they can be tested locally with the results promptly communicated to the Investigator site.

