## 14. APPENDICES

### Appendix 1: Schedule of Assessments (SoA)

Study Event	Scr.  (D-28 to -1)	Study Assessments per Planned Study Day						EOS
		D1 	D3	D14±2 W2	D28±2 W4	D56±2 W8	D84±2 EOT  /W12	D112±2 W16
ICF  ; Demography; Medical History	x							
Inclusion/Exclusion	x							
FSH  ; HIV/HCV/HBV	x							
AMA/M2/PBC-ANAb 	x							
Pregnancy Test 	x	x			x	x	x	x
Height  , Weight, BMI	x							x
PT/PTT and INR	x							x
Oral Temperature	x	x						x
Physical Exam 	x	x	x	x	x	x	x	x
Vital Signs 	x	x	x	x	x	x	x	x
ECG	x	x	x		x		x	
Safety Lab. Tests 	x	x	x	x	x	x	x	x
PBC-40 QoL		x			x	x	x	x
VAS and 5-D Itch		x			x	x	x	x
Biomarkers (FGF19, C4, BA) 		x		x	x	x	x	
CV Markers 		x		x	x	x	x	x
Fibroscan	x							
ELF panel, PRO-C3, Inflammatory Markers 	x	x					x	
APRI, FIB-4		x					x	
PK/PD Substudy (PK, C4, FGF19, BA, ALP) 		x		x	x	x	x	
Population PK Samples 		x		x	x	x	x	
Dispense Study Drug		x			x	x		
Study Drug Dosing 		daily dosing						
Drug Accountability			x	x	x	x	x	
AEs & Con Meds 	x	x	x	x	x	x	x	x

 Screening assessments should be conducted within 28 days prior to the first dose of study drug (ie, Study Days -28 to -1)

 On Day 1, all samples are to be collected predose with the exception of respective post-dose PK and PD samples

 Subjects should discontinue drug on Day 84. Subjects who return for their EOT Visit after Day 84, should stop dosing on Day 84.

 For the treatment phase, indicates number of completed weeks of treatment

 Subjects who discontinue treatment early should complete the EOT procedures as soon as possible and return 4 weeks later for the EOS visit

 Informed consent must be obtained prior to conducting any study-specific procedures or assessments

 For post-menopausal women only

 Only if historical values are not available; one test must be positive for study entry to confirm PBC diagnosis (see Inclusion Criterion #3)

 Serum pregnancy test at Screening and Baseline, and urine pregnancy testing at Baseline and all other visits. If the urine pregnancy test is positive, a serum pregnancy test should be obtained as soon as possible to confirm.

 Height should only be measured at Screening

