9.2.2.1 Enhanced Liver Fibrosis (ELF) Panel

The ELF panel combines 3 biomarkers that have been shown to correlated with the level of liver fibrosis assessed by a liver biopsy. These biomarkers include HA, PIIINP, and TIMP 1.

A descriptive summary will be provided for noninvasive liver fibrosis markers (ELF panel) values, change from Baseline and percentage change from Baseline using 8-number summary by visit and treatment group.

Change from Baseline and percentage change from Baseline at week 12 will be analyzed using an ANCOVA model with treatment as fixed effect and the associated baseline value as covariate. Least squares means and standard errors will be presented for each visit, p-value and 2-sided 95% confidence interval for treatment differences will be presented for each visit. Significance tests will be based on least-squares means using a two-sided $\alpha = 0.05$.

A by-subject listing will be provided for observed and derived variables.

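### Twice-drawn liver, fibrosis and inflammation markers are adjusted for one pre-dose value; adding the Screening value as a second ANCOVA covariate would probably narrow most Week 12 intervals a little, at almost no cost

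*SAP*

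**What the plan says.** SAP 6.2 gives three baseline definitions for the primary ALP endpoint. Method 1, its main definition, is "the average between the screening and the day 1 visits. If either is missing, the non-missing value will be considered baseline for this approach". Method 2 is "The Day 1 value or the last value prior to first dose of study drug". Method 3 is the Screening value. Everything else gets method 2: "For all secondary and safety endpoints, baseline will be defined using method 2.) above". The SAP gives no reason for the difference.

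The schedule of assessments (protocol Appendix 1, repeated in SAP Appendix 5) marks the safety laboratory row, which carries bilirubin, ALT, AST and GGT, at Screening and Day 1. The row "ELF panel, PRO-C3, Inflammatory Markers" is marked at Screening, Day 1 and Week 12. APRI and FIB-4 are marked at Day 1 and Week 12 only. FGF19, C4, bile acids, the cardiovascular markers, the itch scales and PBC-40 have no Screening entry.

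The planned analysis of each marker (SAP 9.2.1 to 9.2.4; the wording here is from 9.2.2.1) is an "ANCOVA model with treatment as fixed effect and the associated baseline value as covariate".

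The protocol has two statements on baseline. Section 7.1.3, on Day 1: "Predose assessments and procedures will be conducted as noted in the SoA (Appendix 1) and considered Baseline values". Section 10.2, on liver enzyme elevations: "To establish a baseline utilizing at least 2 lab values at least several weeks apart".

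**The concern.** For these markers the trial collects two pre-treatment samples, both fasting and both analyzed by the central laboratory (protocol 8.3 and 8.3.1), and adjusts for one. ELF, PRO-C3 and the inflammatory markers appear in no eligibility criterion. Their Screening sample therefore does nothing in the planned efficacy analysis unless Day 1 is missing.

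What is at stake is precision. Placebo has 15 planned completers (about 17 enrolled, since 119/7 = 17), so every active-versus-placebo contrast is wide. In ANCOVA the benefit of a baseline depends on how well it predicts Week 12. A single noisy value predicts less well than two values do, unless the earlier one adds nothing.

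**Working it through.** **The plan's own figure.** There is none to reproduce. The only stated power concerns the primary ALP responder endpoint. No SD, correlation or power is given for the secondary markers, so every correlation below is an assumption.

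**Inputs.** Planned sizes 45, 45 and 15 (protocol 11.2). Write r1 for the correlation of Day 1 with Week 12, r0 for Screening with Week 12, and r12 for Screening with Day 1. Take equal variance at each visit.

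**Residual variance, as a fraction of outcome variance**
- Day 1 only: 1 − r1²
- Mean of the two values: 1 − [(r1 + r0)/2]² / [(1 + r12)/2]
- Both as covariates: 1 − (r1² + r0² − 2·r1·r0·r12)/(1 − r12²)

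The ratio of standard errors (SEs) is the square root of the ratio of residual variances. With Day 1 as covariate, modelling change or the Week 12 value gives the same treatment contrast, so the formulas apply to change from Baseline. They do not apply exactly to percent change, for which no figure is offered.

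**Case 1: all correlations equal to r.** The mean and the two-covariate model coincide, with residual variance 1 − 2r²/(1 + r).

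| r | Day 1 only | Both values | SE ratio | SE lower by |
|---|---|---|---|---|
| 0.3 | 0.910 | 0.862 | 0.973 | 2.7% |
| 0.5 | 0.750 | 0.667 | 0.943 | 5.7% |
| 0.7 | 0.510 | 0.424 | 0.911 | 8.9% |
| 0.8 | 0.360 | 0.289 | 0.896 | 10.4% |
| 0.9 | 0.190 | 0.147 | 0.881 | 11.9% |

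At r = 0.7 the 95% half-width for 45 against 15 is 1.96 × √0.510 × √(1/45 + 1/15) = 0.417 SD, falling to 1.96 × √0.424 × 0.298 = 0.380 SD. The variance ratio 0.424/0.510 = 0.83 is worth about 20% more subjects.

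**Case 2: Screening predicts Week 12 less well than Day 1.** Take r12 = 0.8 and r1 = 0.7, so Day 1 alone leaves 0.510.

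| r0 | Mean: residual, SE ratio | Both covariates: residual, SE ratio |
|---|---|---|
| 0.70 | 0.456, 0.945 | 0.456, 0.945 |
| 0.65 | 0.494, 0.984 | 0.488, 0.978 |
| 0.60 | 0.531, 1.020 | 0.506, 0.996 |
| 0.56 | 0.559, 1.047 | 0.510, 1.000 |

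Averaging breaks even at r0 = 2 × 0.7 × √0.9 − 0.7 = 0.63. Below that it loses. The last row has r0 = r1 × r12 = 0.7 × 0.8, the case in which Day 1 already carries everything Screening knows about Week 12. There the second covariate gains nothing, and averaging costs 4.7%.

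**Case 3: a mixed structure.** Assume half the variance is stable between subjects, 0.3 drifts with a 12-week half-life and 0.2 is visit noise, with Screening 4 weeks before Day 1.
- r1 = 0.5 + 0.3 × 0.5 = 0.650
- r12 = 0.5 + 0.3 × 2^(−4/12) = 0.738
- r0 = 0.5 + 0.3 × 2^(−16/12) = 0.619

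Day 1 alone leaves 1 − 0.650² = 0.578. The mean leaves 1 − 0.6345²/0.869 = 0.537. The SE ratio is √(0.537/0.578) = 0.96.

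**Cost of the extra covariate.** In one model over 105 subjects, residual degrees of freedom go from 105 − 4 = 101 to 100. If Screening were uninformative, the variance would rise by about 1/100, or roughly 0.5% in the SE. If each active arm were modelled only with placebo (60 subjects), they go from 57 to 56, or roughly 0.9% in the SE.

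**The case against.** The strongest defence is that method 2 is the protocol's definition. Section 7.1.3 makes the Day 1 predose values Baseline. The endpoint wording also separates the cases: the primary endpoint is measured against pretreatment values, the secondary ones against Baseline. This stands. SAP 6.2 does not contradict protocol 7.1.3, and replacing Day 1 with the two-visit mean in the main analysis would depart from the protocol's Baseline.

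A reader might also infer that averaging would tighten every Week 12 comparison. The documents do not support that. They give no correlations, Screening can be up to 28 days before dosing, and Case 2 shows averaging can lose. Nor is the Screening value wholly without use: under method 2 it is the fallback for a missing Day 1. It would also be wrong to say that baseline noise passes straight into the ANCOVA estimate of change. It only weakens the adjustment.

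Screening bilirubin, ALT and AST are limited by eligibility rules, and one retest is possible (protocol 3.1, 3.2 and 7.1.1), so for these markers Screening is not a clean replicate of Day 1. That may lower r0 but cannot bias a randomized contrast, and ALP, itself an entry criterion, is averaged anyway. It does not touch ELF, PRO-C3 or the inflammatory markers.

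Finally, these are Phase 2 secondary endpoints without stated power or multiplicity control, so the consequence is modest. That also stands. None of these arguments defeats keeping the Day 1 Baseline and adding Screening as a covariate.

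**Conclusion.** The plan is valid and unbiased here, but it passes up a cheap gain in precision. Using both pre-dose values would lower the SE by about 6% to 10% if all correlations are equal at 0.5 to 0.8, by about 4% in the mixed case, and by almost nothing if Day 1 already contains the Screening information. These figures rest on assumed correlations and equal variances, and they concern change from Baseline, not percent change.

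Two stronger readings should be resisted: that the single baseline distorts the comparison between arms, and that the method 1 mean should become the main baseline. Randomization rules out the first. The second conflicts with protocol 7.1.3 and could raise the SE by about 2% to 5%. The two-covariate model avoids both problems, and its worst case is roughly the price of one degree of freedom.

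A separate loose end is that protocol 10.2 asks for a baseline from at least two laboratory values, while SAP 6.2 gives safety endpoints, and hence the multiples of Baseline in SAP 10.2.1, a single value. These passages need to be reconciled.

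**What to change.** In SAP 6.2 and 9.2, for the efficacy analyses of bilirubin, ALT, AST, GGT, the ELF components, PRO-C3 and the inflammatory markers:

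- Keep the outcome as change from the Day 1 Baseline (method 2), and add the Screening value as a second covariate. If Screening is missing, enter the Day 1 value in its place.
- Use the rule in SAP 10.2 to choose the Screening result: the latest in the Day −28 to Day −1 window.
- Report the current single-baseline model as a sensitivity analysis and, optionally, a model using the method 1 mean.
- Leave unchanged the safety baselines, APRI and FIB-4 (not scheduled at Screening) and all markers drawn before dosing only on Day 1.

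Separately, state how the two-value baseline in protocol 10.2 relates to SAP 6.2, and align the two texts.

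The cost is one degree of freedom per model, one extra column in the analysis datasets and slightly more analysis work. No new samples are needed. The SAP provides for amendment until database lock, so the change should be specified before then.

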6.3 Study Day Windows

The windows for all visits including PK draws appear in table below:

Visit	Target Day	Time window
Screening	Day -1	Day -28 to Day -1
Day 1	Day 1	N/A
Day 3	Day 3	N/A
Week 2	Day 14	Day 4 to Day 21
Week 4	Day 28	Day 22 to Day 42
Week 8	Day 56	Day 43 to Day 70
Week 12	Day 84	Day 71 to less than or equal to End of Treatment+7 days
Treatment-Free Follow-up Week 4	Day 112	Greater than End of Treatment+7 days to last visit

- Samples at each visit should be obtained at different times postdose relative to each of the other visits (2, 4, and 8)
- The target day for the screening visit is Day -1 during the period of Day -28 to Day -1

The relative day will be computed for each laboratory, vitals, ECG and PD data point. The relative day will be calculated as visit date-date of first dose+1. For data collected prior to first dose, the relative day will be calculated as visit date-date of first dose. When there are multiple observations within a visit window, the value closest to the target day will be analyzed..

PK/PD Draw Timing

Visit	Target Day	PK/PD Substudy (PK, C4, FGF19, BA, and additional ALP samples)	Population	
			For subjects not substudy	
			PK	PD (FGF19, BA, C4)
Day 1	Day 1	At predose and 2, 6, and 8 hr postdose	at predose and two samples postdose; 
 • First sample collected 1 to 3 hours postdose • Second sample at least 1 hour later 	At predose
Week 2	Day 14	at predose and two samples postdose; 
 • First sample collected 1 to 3 hours postdose • Second sample at least 1 hour later 	at predose and two samples postdose; 
 • First sample collected 1 to 3 hours postdose • Second sample at least 1 hour later 	At predose
Week 4	Day 28	at predose and two samples postdose; 
 • First sample collected 1 to 3 hours postdose • Second sample at least 1 hour later 	at predose and two samples postdose; 
 • First sample collected 1 to 3 hours postdose • Second sample at least 1 hour later 	At predose
Week 8	Day 56	at predose and two samples postdose; 
 • First sample collected 1 to 3 hours postdose • Second sample at least 1 hour later 	at predose and two samples postdose; 
 • First sample collected 1 to 3 hours postdose • Second sample at least 1 hour later 	At predose
Week 12	Day 84	At predose and 2, 6, and 8 hr postdose	at predose and two samples postdose; 
 • First sample collected 1 to 3 hours postdose • Second sample at least 1 hour later 	At predose

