#### **7.1.5 Safety Follow-up Period (End of Study Visit)**

All subjects, including those who discontinue treatment early, should return to the clinic for the End of Study (EOS) visit 4 weeks after the last dose of study drug for safety assessments (Appendix 1). For subjects who complete the study, the EOS visit would be scheduled on Day 112. Following completion of study procedures, subjects will be terminated from the study.

Any subject with ongoing AEs/SAEs (serious adverse events) at the EOS visit should be followed until resolution of their AE/SAE or until the Investigator has determined that the event has stabilized as discussed in Section 9.3.

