9.1.3 Imputation of Missing Data

To account for missing data, a sensitivity analysis will be performed using the multiple imputation Markov Chain method.

MMRM Using Multiple imputation (MI)

To assess robustness of the efficacy analysis, sensitivity analysis with missing values imputed by MI will be performed on ALP change from baseline data. In the first stage, missing values will be imputed by Markov Chain Monte Carlo (SAS PROC MI, MCMC) to make the missing pattern monotone (by filling in

imputed values of ALP between 2 non-missing values). In the second stage, monotone linear regression will fill in missing values through Week 12. SAS PROC MI and PROC MIXED will be used to obtain MMRM estimates of treatment difference. SAS PROC MIANALYZE will be used to combine estimates and to generate the average test statistics for hypothesis testing. The Missing at Random method will be used with the following parameters MAR – assume missing at random, number of imputation=100, seed=SEED11 (for MCMC) and SEED12 (for MONOTONE REG) for imputation.

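### Read literally, SAP 6.3 places the off-drug end-of-study values of subjects who stop by about Day 42 in the Week 4 or Week 8 window as well as in follow-up, because only Week 12 is capped at End of Treatment + 7 days

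*SAP*

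**What the plan says.** The window table in SAP 6.3 gives Week 4 as "Day 22 to Day 42" and Week 8 as "Day 43 to Day 70", with targets of Day 28 and Day 56. Neither refers to end of treatment. Week 12 is "Day 71 to less than or equal to End of Treatment+7 days". Follow-up is "Greater than End of Treatment+7 days to last visit", with no minimum study day.

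Study day is counted from first dose: "The relative day will be calculated as visit date-date of first dose+1". The only selection rule is "When there are multiple observations within a visit window, the value closest to the target day will be analyzed".

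Protocol 7.1.5 times the EOS visit at four weeks from the final dose for every subject, early stoppers included. The schedule of assessments allows ±2 days.

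The windowed values feed the responder summary and plot by visit (SAP 9.1.2) and the treatment differences presented at each visit (SAP 9.1.4 and 9.2). They also feed the ALP sensitivity analysis in SAP 9.1.3, where "In the second stage, monotone linear regression will fill in missing values through Week 12".

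**The concern.** An early stopper's EOS visit can fall on a study day that belongs to an on-treatment visit. The printed table then assigns one off-drug value to both that visit and follow-up.

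This conflicts with the SAP's own convention. The Week 12 window ends at End of Treatment + 7 days, and SAP 10.1 counts adverse events as on-treatment up to 7 days after last dose. Weeks 2, 4 and 8 have no such limit.

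By-visit estimates would mix on-drug and off-drug values. In SAP 9.1.3, a Week 4 or Week 8 ALP taken four weeks after stopping would count as observed and could help predict the imputed Week 12 value. Early stoppers are the very subjects whose Week 12 value has to be imputed.

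**Working it through.** **Inputs.** Windows from SAP 6.3; EOS = last dose + 28 days from Protocol 7.1.5; tolerance ±2 days from the schedule of assessments; 10% discontinuation and 119 enrolled against a target of 105 from SAP section 5.

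**The plan's own figure.** A completer stops on Day 84: 84 + 28 = Day 112, the EOS day in the protocol.

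**Mapping.** Let L be the day of last dose. Nominal EOS day = L + 28, which always exceeds L + 7, so the follow-up definition is always met.

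| Last dose (Day) | EOS (Day) | Windows met |
|---|---|---|
| 1-14 | 29-42 | Week 4 and follow-up |
| 15-42 | 43-70 | Week 8 and follow-up |
| 43-84 | 71-112 | Follow-up only |

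So 42 of 84 possible stopping days produce an overlap. EOS never falls in Week 2: its earliest day is 29, or 27 with the tolerance. It never falls in Week 12, which is capped. An EOS visit 2 days early moves the two upper limits to Day 16 and Day 44; 2 days late moves them to Day 12 and Day 40.

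**Which value is selected.** If the EOT visit is on the day of last dose, EOS is the value closest to target for all 42 stopping days. If the EOT visit is 1-7 days later, EOS is selected for 38 to 41 of the 42. The exceptions lie among stops on Days 39-42, where the EOT visit is itself in the Week 8 window and nearer Day 56.

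**Filling or displacing.** For stops on Days 1-35, an EOT visit within 7 days of last dose is in an earlier window, so EOS fills an otherwise empty cell. EOS strictly beats an EOT value in the Week 8 window only for stops on Days 36-40 with the EOT visit 3-7 days later, on Days 43-45. Example: last dose Day 40, EOT visit Day 43, EOS Day 68. The distances from Day 56 are 13 and 12, so EOS is chosen. With dropout spread evenly, the number stopping on Days 36-40 is 12 × 5/84 = 0.7 to 14 × 5/84 = 0.8, and only those with a late EOT visit count.

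**Number exposed.** Discontinuations are 0.10 × 119 ≈ 12, or 119 − 105 = 14. The share stopping by Day 42 is not given, so it is an assumption, as is full EOS attendance:
- a quarter: 3.0 to 3.5, about 3-4 subjects
- half: 6 to 7
- three quarters: 9 to 10.5, about 9-11

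**Data exposed.** EOS collects safety chemistry (including ALP, bilirubin, ALT, AST and GGT), lipids and CV markers, and vital signs. PBC-40 and itch scores are also collected; they are affected only if the same windows are applied, since the relative-day rule names laboratory, vital-sign, ECG and PD data. FGF19, C4, bile acids, ELF, PRO-C3, the inflammatory-marker panel, APRI, FIB-4, ECG and PK are not scheduled at EOS.

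**After the change.** With the earlier windows also ending at End of Treatment + 7 days, EOS falls in an on-treatment window for 0 of 84 stopping days.

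**The case against.** The strongest reply is that the SAP never says one record is analysed at two visits. It names a treatment-free follow-up window defined relative to end of treatment, and a programmer could sensibly give that window precedence. This stands in part: double use is the literal result of overlapping windows, not a stated rule. But the SAP gives no precedence, and the printed day ranges admit the value.

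A second reply is that keeping off-drug values is an estimand choice, since the efficacy set is by randomised arm and the SAP states no estimand. The table does not carry that choice through. A subject stopping on Day 42 has EOS on Day 70, inside Week 8. One stopping on Day 43 has EOS on Day 71, barred from Week 12 because that window would end at Day 50. Off-drug data are used or excluded by accident of stopping day, which fits neither an on-treatment nor a treatment-policy approach.

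Some stronger readings are tempting but unsupported:
- *Every early stopper is affected.* The subject must attend EOS, and Protocol 7.2 provides for loss to follow-up and withdrawal of consent. Day 42 is not a sharp edge either: besides the ±2 days, a schedule footnote can be read as timing EOS from the EOT visit.
- *On-treatment values are routinely overwritten.* That is a corner case.
- *The bias follows from drug half-life.* At the 10-23 hours reported in Protocol 1.4.1, 28 days is at least 672/23 ≈ 29 half-lives, so the drug has gone. Plasma half-life does not say how fast ALP returns, and the documents give no such data.
- *The primary analysis is compromised.* It is not. The SAP 9.1.3 analysis concerns continuous ALP change, not the responder comparison itself.

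**Conclusion.** The overlap is real on the printed text and should be corrected, but its reach is limited. It rests on a literal reading of the windows, EOS at about last dose + 28 days, and attendance at that visit.

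The Week 12 responder result is unaffected: subjects stopping by about Day 42 have no Week 12 value and count as non-responders either way. The by-visit responder summary, the earlier-visit ANCOVAs for data collected at EOS, and the ALP imputation/MMRM sensitivity analysis are exposed. Plausibly 3 to 11 subjects are involved, depending on how early dropouts occur. No numerical effect on any estimate can be derived from the documents.

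**What to change.** In SAP 6.3, add *and not later than End of Treatment + 7 days* to the Week 4 and Week 8 windows, and to Week 2 for consistency. Alternatively, state that the follow-up window takes precedence. Either way, values after End of Treatment + 7 days go to follow-up only. It would also help to say whether End of Treatment means last dose or the EOT visit, and whether the windows apply to PBC-40 and itch scores.

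The core change is one phrase in the window table. It needs no new data, extends a rule the SAP already uses, and leaves the Week 12 primary result unchanged.

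### SAP 6.3 fixes the four-week follow-up target at Day 112 for everyone and gives Day 3 no window, so some results can be summarised under the wrong visit

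*SAP*

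**What the plan says.** SAP 6.3 introduces its table with "The windows for all visits including PK draws appear in table below". Days are counted from first dose: "The relative day will be calculated as visit date-date of first dose+1". The scope is wide: "The relative day will be computed for each laboratory, vitals, ECG and PD data point". The rows are:

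- Day 1 and Day 3: window N/A.
- Week 2: Days 4 to 21, target 14.
- Week 4: "Day 22 to Day 42", target 28.
- Week 8: Days 43 to 70, target 56.
- Week 12: Day 71 to End of Treatment + 7 days, target 84.
- Four-week treatment-free follow-up: "Greater than End of Treatment+7 days to last visit", target 112.

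The selection rule is "When there are multiple observations within a visit window, the value closest to the target day will be analyzed".

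Protocol 7.1.5 says that all subjects, early stoppers included, "should return to the clinic for the End of Study (EOS) visit 4 weeks after the last dose of study drug". It names Day 112 only for those who complete. Results later than EOS are possible. Protocol 7.1.5 and 7.2 follow ongoing adverse events until they resolve or stabilise, and protocol 10.2 says of persistent transaminase elevations "Repeat liver enzyme and serum bilirubin tests two or three times weekly", with a lower frequency allowed later, including after the drug is stopped.

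The schedule of assessments (protocol Appendix 1, SAP Appendix 5) has laboratory tests, vital signs and an ECG on Day 3. It gives that visit no tolerance, while later visits have ±2 days. No ECG is scheduled at Week 2.

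**The concern.** The follow-up row is labelled as four weeks off treatment, but its target is anchored to first dose. For a subject who stops early, the label and the target refer to different days, and a nearest-to-target rule then pulls towards later results. The same row opens 7 days after End of Treatment with no statement that the Week 4 and Week 8 windows close at that point, so one off-drug result can belong to two windows. At the other end of the table, a Day 3 visit that slips by a day has no place of its own.

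At stake is whether by-visit tables show what their column headings say: follow-up values four weeks off drug, Week 4 and Week 8 values on drug, and Day 3 values as the first on-treatment assessment.

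**Working it through.** Let L be the study day of last dose. I take End of Treatment to mean L; SAP 6.3 does not say whether it means last dose or the end-of-treatment visit.

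**1. The plan's own figure.** For a completer, L + 28 = 84 + 28 = 112, which reproduces the SAP target. For an early stopper, the fixed target is 112 − (L + 28) = 84 − L days too late:

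| L | L + 28 | 84 − L |
|---|---|---|
| 14 | 42 | 70 |
| 30 | 58 | 54 |
| 42 | 70 | 42 |
| 56 | 84 | 28 |
| 70 | 98 | 14 |

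**2. Which value is picked.** An early stopper has an end-of-treatment visit as soon as possible and then EOS at L + 28.

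- Suppose the end-of-treatment visit is late enough to fall in the follow-up window, say at L + 10. Its distance from Day 112 is 102 − L, against 84 − L for EOS, so EOS is picked. A result at L + 21 (distance 91 − L) also loses for every early stopper.
- A result after EOS can win. One at L + 35 beats EOS when the midpoint of the two, L + 31.5, is below 112, that is for L up to 80. One at L + 42 beats EOS when L + 35 is below 112, that is for L up to 76.
- With a target of L + 28, EOS is kept in all these cases.

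**3. Overlap with on-treatment windows.** EOS falls on L + 28.

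- L = 1 to 14: Days 29 to 42, inside both follow-up and Week 4.
- L = 15 to 42: Days 43 to 70, inside both follow-up and Week 8. For L = 28, EOS is Day 56, exactly the Week 8 target.
- L = 43 to 84: Days 71 to 112, follow-up only, because the Week 12 window ends at L + 7.

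**4. Day 3, with windows applied by relative day.**

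- A visit on Day 2 falls in no window.
- A visit on Day 4 or 5 falls in Week 2, 10 or 9 days from the target of 14. A Week 2 visit on Days 12 to 16 is at most 2 days away, so the early laboratory values lose to it. If the Week 2 visit is missed, they stand as Week 2.
- An ECG on Day 4 or 5 has no scheduled Week 2 ECG to compete with and is summarised as Week 2.

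If N/A means that the nominal visit label is kept, none of this step occurs. The SAP does not say which reading applies.

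**5. Where it can show.** SAP 9.1.4, 9.2.1 and 9.2.5 give by-visit summaries and by-visit p-values for ALP, bilirubin, ALT, AST, GGT and lipids, all of which are drawn at EOS. SAP 10.3 and 10.5 summarise vital signs and ECGs by time point. The responder endpoint in SAP 9.1.1 uses Week 12. SAP 10.2 tabulates safety laboratory results at Baseline and Week 12. Neither depends on the follow-up target, the Day 3 row or the Week 4 and Week 8 overlap.

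**The case against.** The strongest reply is that the follow-up rule works on the protocol's own schedule: EOS is an early stopper's last scheduled visit, so nearest to Day 112 selects it. That is correct, and it means the target does harm only when a result exists after EOS.

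Such results are also limited. Protocol 7.1.5 ends participation after EOS, so the last visit that closes the window could be read as EOS itself. Protocol 9.3 caps the wait for stabilisation at 30 days after the event. These points narrow the problem without closing it. The SAP does not define last visit or exclude unscheduled results, and an event starting 10 days after last dose could be followed to day 10 + 30 = 40 off drug, past EOS at 28. The cap does not apply to events still resolving.

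For Day 3, it is fair to say that N/A matches a visit without tolerance, that Day 1 is treated the same way, and that a nominal label is a natural reading. This stands as an alternative, but the SAP should state it, because it also says that a relative day is computed for every laboratory, vital-sign and ECG value.

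A reader might infer that liver abnormalities would look more resolved at follow-up than they were, and might try to put a factor on it. The documents give neither the number of post-EOS results nor any rate of recovery, so neither the direction across an arm nor the size can be supported. Liver signals are also captured separately, through the incidence categories in SAP 10.2.1. A reader might also infer that Day 3 data are lost. They are not: laboratory, vital-sign and ECG values are all listed, and the QTcF thresholds in SAP 10.5 use maximum values.

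**Conclusion.** The point holds as a minor defect in the visit-window rules. The Day 112 target agrees with the protocol only for completers. It leaves the scheduled EOS value in place and can displace it only when an early stopper has a later result. For last doses on Days 1 to 42, the EOS value also qualifies for an on-treatment window. The Day 3 problem depends on windows being applied by relative day and disappears if the nominal label is kept.

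By-visit summaries and nominal by-visit tests are exposed. The Week 12 primary endpoint and the Baseline and Week 12 safety laboratory tables are not affected.

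The number of subjects cannot be derived. The planned 10% discontinuation implies about 0.10 × 119 = 12 early stoppers, but not how many stop by Day 42 or have a result after EOS. The share of Day 3 visits made on another day is not given either. The arithmetic assumes that End of Treatment means last dose.

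**What to change.** In SAP 6.3:

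- Set the follow-up target to last dose + 28 days for every subject. For completers this remains Day 112.
- Assign values more than 7 days after last dose only to follow-up, never to Week 2, Week 4 or Week 8. Changing the target alone would leave the overlap for last doses on Days 1 to 42.
- Either give Day 3 a window or state that it keeps its nominal visit label. A possible window is Day 2 to Day 8, with Week 2 from Day 9, since the midpoint of the targets is (3 + 14)/2 = 8.5. The Week 2/4 and Week 4/8 boundaries follow the same pattern: (14 + 28)/2 = 21 and (28 + 56)/2 = 42. It is not a general rule of the table, because the boundary between Week 12 and follow-up is set at End of Treatment + 7 days. It would also label a Day 8 value as Day 3, so the nominal label is a reasonable choice.
- State that End of Treatment in this table means last dose.

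The cost is a few lines in one SAP section and the matching derivation, made before database lock. No new data are needed.
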